Document date: 2/26/2022

NCT number: NCT05143801

Official Title:

Facemask use during high intensity interval exercise in temperate and hot environments.

Objectives, Methods and Protocol

Objective: The purpose of this study was to investigate the effects of surgical mask use during high intensity interval exercise (HIE) on physiological and perceptual responses in hot and temperate environments.

Methods, Protocol, and Statistical Analysis

Participants

Ten recreationally trained participants (5 males; 5 females) were recruited for this study (Table 1). Participants were free from known cardiovascular, renal, metabolic, or chronic respiratory disease (i.e., asthma) as determined from a health history questionnaire. Participants were excluded if in the last 6 months they smoked and performed less than 150 minutes of moderate-intensity exercise per week, had a $\text{VO}_{2\text{max}}$ below the 50th percentile for age and sex according to the ACSM guidelines for aerobic fitness ¹⁸, or reported no experience performing HIE. A pregnancy test was completed for female participants to include only non-pregnant participants.

Prior to any exercise and data collection, the study protocol was explained, all participant concerns were addressed, and written consent was obtained. This study was registered at Clinicaltrials.gov (NCT05143801), approved by the university's Institutional Review Board, and was in compliance with the Declaration of Helsinki ¹⁹.

Prior to each visit the participant was screened through ZoomTM (Zoom Video Communications, Inc, Version 5.4.9), email, or by phone for possible exposure to, and symptoms of COVID-19 using a screening checklist. Additionally, they were instructed to avoid eating a filling meal 1-hour, consuming caffeine 4 hours, and vigorous exercise 24 hours before the first visit.

Procedures

Anthropometrics and maximal Oxygen uptake measurements

Before the experimental trials, participants visited the Exercise Physiology laboratories for anthropometrics and $\text{VO}_{2\text{max}}$ measurement. Body height was measured using a stadiometer (SECA, seca 216, Chino, CA, USA) and weight was measured using a digital scale (Cardinal DETECTO 758C, Webb City, MO). Then, participants completed a 5-minute warm-up at a self-selected exercise intensity prior to the $\text{VO}_{2\text{max}}$ test on an electrically braked cycle ergometer

(Lode, Excalibur Sport, Groningen, The Netherlands). During the VO₂max test, HR was measured using a Polar HR monitor (Polar, Polar H10, USA) with each test designed to last between 10 and 12 minutes. The starting resistance and the continuous increase in resistance (between 20-40 watts) throughout the test was based on the participants' self-reported fitness. Termination of the VO₂max test occurred at volitional fatigue or when the participant could no longer maintain a cycling cadence of 60 revolutions per minute or higher. Gas-exchange was measured using a metabolic analyzer (Parvo Medics Inc, TrueOne 2400, Salt Lake City, UT) and data were analyzed using an 11-breath rolling average²⁰. Primary criteria for a VO₂max was categorized as an observed plateau that varied by less than 150 mlO₂/min²¹. To determine a plateau using primary criteria, the mean of the absolute difference from each neighboring data point in the last 30 seconds of the 11-breath rolling average VO₂ was compared against 150 mlO₂/min²¹; if the average value was smaller, the test was categorized as a VO₂max. In the absence of a plateau, a VO₂max was confirmed if two of the three secondary criteria were met: 1) an RPE ≥ 17 , 2) a respiratory exchange ratio (RER) of 1.1 or greater, and 3) a HR within 10 beats of estimated heart rate max using the Jones et al.²² equation (202 - 0.72 x age). The highest power output recorded from the VO₂max test was used to calculate the high intensity and active recovery bouts for the HIIE sessions.

Environmental control

All trials were performed indoors within the University of New Mexico exercise physiology lab. The environmental conditions for all trials were monitored using the same wet bulb globe temperature (WBGT) device (Metrosonics, hs-3600 Portable Heat Stress Monitor, QUEST TECHNOLOGIES INC., GA, USA). Dry and wet bulb temperatures were recorded at the end of each active rest and HIIE bout for each trial.

A heat chamber with two electric heaters connected to a thermostat set to 36°C was used for both HIIE-HOT/CON and HIIE-HOT/MASK trials. This room was ventilated with the use of a ceiling fan set to low and by having the door slightly open. To control for any deviations in room temperature additional heaters were placed in the room and manually controlled to keep the room temperature stable. Humidity buildup in the heat chamber was prevented by having the door slightly open to allow humidity to escape the room.

Both HIIIE-TEMP/CON and HIIIE-TEMP/MASK trials were performed in a well-ventilated room. The room temperature was controlled for using the same methods for the HIIIE-HOT/CON and HIIIE-HOT/MASK trials.

High Intensity Interval Exercise Trials

Before all HIIIE sessions participant's hydration status was assessed measuring urine specific gravity (USG) using a handheld refractometer (Cole-Parmer, RSA-BR90A, Vernon Hills, IL). A USG measurement lower than 1.020 g/cc allowed participants to proceed to the HIIIE sessions. If USG was greater than 1.020 g/cc, then participants consumed 500 ml of water, and were reassessed after 30 minutes. This water provision was only repeated twice if USG remained above 1.020 g/cc.

A randomized non-counterbalanced crossover repeated measures design was used to compare cardiovascular, thermoregulatory, metabolic, and perceived responses before and during HIIIE across four experimental trials performed during two visits. For each visit, which was separated by a minimum of 72 hours, the participants completed two HIIIE sessions separated by 3 hours of rest. Each HIIIE bout consisted of 10 bouts lasting 30 seconds performed at 85% P_{max} followed by 90 seconds of active recovery at 30% P_{max} . The HIIIE sessions were performed in a temperate environment (23°C, 25% relative humidity) with (TEMP/MASK) and without a surgical mask (TEMP/CON), and in a hot environment (36°C, 14% relative humidity) with (HOT/MASK) and without a surgical mask (HOT/CON). During the exercise protocol participants were allowed to drink water. Although most participants chose not drink water during all HIIIE sessions, one participant chose to ingest water during two of the four HIIIE sessions while another participant chose to ingest water during one of the four HIIIE sessions.

During HIIIE sessions with a mask, all participants were instructed to wear the surgical mask snuggly over their nose and mouth. The participants fitted the flexible metal plate within the surgical mask over the bridge of the nose and had the bottom of the mask cover underneath the chin. During the 3-hour rest period participants were provided a 350-calorie meal (7g of Fat; 64g Carbohydrate; 9g Protein) and water *ad libitum*.

Cardiovascular Measurements

Before every HIEE trial and after 5-minutes of seated rest, resting blood pressure was measured using a sphygmomanometer, and stethoscope. A cardiac impedance device (PhysioFlow®, NeuMeDex, Bristol, PA) calibrated per manufacturer guidelines was used to indirectly measure cardiac output (CO), stroke volume (SV), and HR. These measurements were taken continuously using 10-second averaging provided by the PhysioFlow® software during each HIEE session.

Metabolic Measurements

A near infra-red spectroscopy (NIRS) device (Moxy, Moxy Monitor System, MN, USA) was used to measure muscle tissue oxygenation every second during each HIEE session. The highest muscle tissue oxygenation value from each active rest period (MTO active rest %) was averaged for each HIEE session. Additionally, the lowest muscle tissue oxygenation (MTO during HIEE %) value per high intensity bout was recorded and averaged from each HIEE session. The difference of the average MTO active rest % and MTO during HIEE % was used to calculate the muscle tissue oxygenation difference (MTO difference %). All MTO measurements were taken on the dominant leg at a marked location on the *vastus lateralis* that would allow movement without interference from the NIRS device. A pulse oximeter (Caretaker, Caretaker Medical, USA) was used to measure SpO₂ during HIEE. Blood lactate measurements (Lactate Plus, NOVA Biomedical, MA) were taken in duplicate at the ear lobe immediately before, and 5-minutes post HIEE.

Perceptual Measurement before and during HIEE

Borg's rating of perceived exertion (6 rest to 20 maximal effort) scale (RPE)²³ and thermal sensation (0 very cold to 8 very hot)^{24,25} was measured immediately before and every four minutes into HIEE. A breathlessness scale (0 mm no breathlessness to 200 mm maximal breathlessness)²⁶ was used immediately before, at 10-minutes, and immediately after exercise to record subjective change in difficulty breathing. The highest measurements for both RPE (peak RPE) and thermal sensation (peak thermal sensation) were recorded per HIEE session performed. Additionally, RPE (RPE avg) and dyspnea scores were averaged over time for every HIEE session.

Thermal strain and hydration measurements

During each HIE exercise session continuous core temperature measurements were taken using rectal thermistors (Level 1 esophageal/rectal temperature probe, Smiths Medical, Minneapolis, MN, USA) connected to a thermometer (Precision 4000, YSI Incorporated, Yellow Springs, OH, USA) and monitored to ensure participant safety. Additionally, Δ core temperature (i.e., the difference between peak core temperature and core temperature prior to starting exercise) and peak core temperature were recorded for each HIE session. Sweat rate and dehydration were calculated from pre-exercise nude weight, post-exercise nude weight, water ingestion, and post-exercise urine output measurements²⁷. Participants were asked to measure and report their pre-exercise and post-exercise nude weight using a digital scale (Cardinal DETECTO 758C, Webb City, MO) in a private room.

Statistical Analysis

Female and male descriptive data in terms of mean and standard deviation (SD) were compared using an independent t-test. If normality was violated, a non-parametric Mann-Whitney U test was performed. A 2x2 repeated measures ANOVA was performed to investigate statistical differences for all variables across TEMP/CON, TEMP/MASK, HOT/MASK, HOT/CON conditions except for a 2x2x3 repeated measures ANOVA being performed for perceived dyspnea data where time was an additional independent variable. Both main and interaction effects were calculated along with effect size, reported as partial η^2 . Effect size benchmarks were defined as small (partial $\eta^2=0.01$), medium ($\eta^2=0.06$), and large ($\eta^2=0.14$)²⁸. A Bonferroni post-hoc test was used to determine specific differences with significant interaction effects. All statistical tests were performed using JASP (version 0.14.1.0); statistical significance was set at $p < 0.05$.

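### As written, the VO2max plateau rule does not separate a plateau from a still-rising VO2, so the secondary criteria would rarely or never be reached; the effect is limited to the VO2max label and its description

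*Combined protocol and SAP*

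**What the plan says.** All of this is in the combined protocol and SAP, section *Anthropometrics and maximal Oxygen uptake measurements*, unless another section is named.

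- **Definition:** "Primary criteria for a VO₂max was categorized as an observed plateau that varied by less than 150 mlO₂/min".
- **Calculation:** the quantity compared with 150 mL/min is "the mean of the absolute difference from each neighboring data point in the last 30 seconds of the 11-breath rolling average" VO2, and "if the average value was smaller, the test was categorized as a VO₂max".
- **Fallback:** "In the absence of a plateau, a VO₂max was confirmed if two of the three secondary criteria were met". The three are an RPE of at least 17, an RER of at least 1.1, and a heart rate within 10 beats of an age-estimated maximum.
- **Test:** the load rises throughout ("the continuous increase in resistance (between 20-40 watts) throughout the test", with no time unit given). "Termination of the VO₂max test occurred at volitional fatigue or when the participant could no longer maintain a cycling cadence" of at least 60 rpm.
- **Use of the test:** "The highest power output recorded from the VO₂max test was used to calculate the high intensity and active recovery bouts". The section *High Intensity Interval Exercise Trials* sets these bouts at 85% and 30% of Pmax.

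The documents give no breathing rate, no breath-to-breath variability and no count of tests that met each criterion.

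**The concern.** A plateau criterion should ask whether VO2 stopped rising while the load kept rising. This calculation asks how far a heavily smoothed curve moves from one breath to the next. Almost any smoothed curve moves little over one breath, whether or not it is climbing. A limit of 150 mL/min, applied to that step, may never bind.

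The order of the criteria makes this matter. The secondary criteria come into play only if the plateau rule fails. If that rule nearly always passes, no independent check that the effort was maximal is made. At stake are the VO2max label, any descriptive fitness values built on it, and how far 85% and 30% of Pmax can be read as fractions of a verified maximum.

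**Working it through.** The documents state no pass rate for this rule, so there is no figure to reproduce.

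**Inputs from the protocol:** 11-breath rolling average; last 30 s; limit 150 mL/min; ramp 20 to 40 W.

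**Assumptions not in the documents:** 30 to 60 breaths/min; ramp expressed per minute; VO2 gain of 9 to 11 mL/min per W; breath-to-breath SD varied from 100 to 1,500 mL/min.

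**Step 1. The statistic.** Let x(i) be the VO2 of breath i and r(i) the mean of breaths i to i+10. Then r(i+1) − r(i) = [x(i+11) − x(i)]/11. The rule passes when the mean of |x(i+11) − x(i)| is below 11 × 150 = 1,650 mL/min.

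**Step 2. Slope alone.** If VO2 rises steadily by b mL/min per minute at f breaths/min, each neighbour difference is b/f.
- Slope needed to fail: 150 × 30 = 4,500 to 150 × 60 = 9,000 mL/min per minute.
- A 40 W/min ramp with no plateau rises 40 × 9 = 360 to 40 × 11 = 440 mL/min per minute. Its statistic is 360/60 = 6 to 440/30 = 14.7 mL/min, against a limit of 150.
- Margin: 4,500/440 = 10.2 to 9,000/360 = 25 times.

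**Step 3. Noise alone.** For independent normal breath noise with SD s, the expected statistic is (2/√π) × s/11 = 0.1026 × s. It reaches 150 at s = 150/0.1026, about 1,462 mL/min.

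**Step 4. Both together.** Simulation of 20,000 tests per setting, at 30, 40, 50 and 60 breaths/min and VO2 slopes of 0, 180, 220, 360 and 440 mL/min per minute:

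| Assumed breath SD (mL/min) | Tests declared a plateau |
|---|---|
| up to 500 | 100% in every setting |
| 800 | at least 99.9% |
| 1,000 | 97.6 to 99.6% |
| 1,200 | 84 to 91% |
| 1,500 | 45 to 48% |

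At SD 200 to 500 the mean statistic is 20.5 to 52.6 mL/min. Autocorrelated noise (−0.3, 0.3 and 0.5, at SD 200 and 500) also gives 100%.

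**Step 5. Discrimination.** At every SD, the pass rates for a flat VO2 and for one rising 440 mL/min per minute agree within about 1 point. Simulation error for such a difference is at most √(2 × 0.25/20,000) = 0.5 point. Where tests fail, they fail on noise and not because VO2 was still rising.

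**The case against.** **The effect on the trial is small.** This stands. Workloads come from the highest power output, not from the plateau verdict, and the 2x2 within-person analyses do not use the label. Stopping at volitional fatigue or at loss of cadence gives partial assurance of effort.

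**The statistic carries some signal.** True. The area under the ROC curve for a 440 mL/min per minute rise against a flat VO2 runs from 0.51 to 0.70. But a cut-off of 150 lies far above the range where that signal sits, so the rule makes no use of it.

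**The result depends on a noise level the documents do not give.** Also true, so no unconditional statement is warranted. The slope margin is at least 10-fold, however, and higher noise does not make the rule discriminate.

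**Neighbouring points could mean non-overlapping 11-breath blocks.** The text describes points of a rolling average. Under the block reading, with a 40 W/min ramp, 10 to 12 mL/min per W and SD 100 to 200, between 28% and 96% of no-plateau tests would still pass.

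**Stronger readings that the documents do not support:**
- *The calculation passes tests that the stated definition would clearly fail, above some ramp rate.* That holds only without noise. At SD 200, a truly flat test meets a range reading of the definition only 36 to 75% of the time, and a ramp of about 20 W/min meets a net-change reading about 73 to 74% of the time. No clean dividing ramp rate exists.
- *Eligibility was compromised.* A submaximal test understates VO2max, so anyone who still cleared the 50th-percentile floor would clear it on a true maximum. Wrongful exclusion is possible in principle, but the documents give no sign of it.
- *Some tests were submaximal.* Nothing shows this; the rule simply cannot vouch that they were maximal.

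**Conclusion.** The point holds, and it is minor. The one-eleventh factor follows exactly from the protocol's wording. The pass rates rest on the assumed breathing rate, VO2 gain, ramp time unit and breath noise. Across the ranges tried, the 150 mL/min rule does not tell a plateau from a continuing rise. That the secondary criteria would rarely or never be reached is an inference from the rule.

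What is affected is the VO2max label, the descriptive fitness values if VO2max is among them (Table 1 is not in the text), and the reading of % Pmax as a fraction of a verified maximum. Wattages, admitted participants and the within-person mask and heat contrasts stay as they are.

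**What to change.** 1. Make no plateau claim from the neighbour-difference statistic.
2. Apply the protocol's existing RPE, RER and heart-rate criteria to all ten stored tests where the data exist, and report how many meet two of the three. Heart rate was recorded ("During the VO₂max test, HR was measured using a Polar HR monitor"), as was gas exchange, which supplies RER. Collection of RPE during this test is implied by its use as a criterion but not stated; the perceptual measurement section covers only the interval sessions. Say so if it is missing.
3. Describe the remaining tests as not verified as VO2max (VO2peak), unless a plateau is shown by a measure of the change in VO2 across the final period, judged against the ramp's expected rise. This keeps a genuine plateau from losing its label merely because fewer than two secondary criteria were met.

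The comparison with the expected rise matters. Suppose the mean of the last 30 s is set against that of the preceding 30 s, with the limit kept at 150 mL/min, a gain of 10 to 12 mL/min per W and SD 100 to 200. Then 0 to 24% of no-plateau tests pass at 40 W/min, and 96 to 100% of flat tests pass. At 20 W/min the expected rise is only 20 × 10 × 0.5 = 100 to 20 × 12 × 0.5 = 120 mL/min, and 66 to 97% of no-plateau tests pass.

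**Cost:** a small re-analysis of ten tests and one or two sentences of text. Some tests may lose the VO2max label. No change to workloads, eligibility or the 2x2 analyses is asked for.

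### The dyspnea ANOVA's mask main effect averages in the resting rating, and the plan defines no ungated estimate of the mask effect during exercise or any sphericity correction (minor)

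*Combined protocol and SAP*

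**What the plan says.** The stated objective is to "investigate the effects of surgical mask use during high intensity interval exercise (HIE) on physiological and perceptual responses in hot and temperate environments". The design paragraph under High Intensity Interval Exercise Trials is wider: it sets out to "compare cardiovascular, thermoregulatory, metabolic, and perceived responses before and during HIIIE across four experimental trials".

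Under Perceptual Measurement, the breathlessness scale (0 to 200 mm) "was used immediately before, at 10-minutes, and immediately after exercise to record subjective change in difficulty breathing". The same section adds: "Additionally, RPE (RPE avg) and dyspnea scores were averaged over time for every HIEE session". It does not say which readings enter the averaged dyspnea score.

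In Statistical Analysis, all outcomes get a 2x2 repeated measures ANOVA, "except for a 2x2x3 repeated measures ANOVA being performed for perceived dyspnea data where time was an additional independent variable". On output and follow-up the section says "Both main and interaction effects were calculated along with effect size" and "A Bonferroni post-hoc test was used to determine specific differences with significant interaction effects". It names no contrast restricted to the exercise ratings, no change from the pre-exercise rating, and no sphericity test or correction.

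**The concern.** Three ratings and a three-level time factor mean that the resting rating is one of the levels. This is inferred from the count, but no other set of three dyspnea ratings exists. The mask main effect is then an equal-weight mean over rest and two later readings, whereas the objective concerns mask use during exercise.

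The mask x time interaction can show that the mask effect differs between rest and exercise. But time-specific testing is tied to a significant interaction. If the interaction is not significant, the one planned mask test left, averaged over environment, is the main effect that includes rest. A reader could then take that figure as the mask effect during exercise, and on the mm scale it generally is not.

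A second, smaller gap is that every effect involving time has a three-level factor. The F test for such effects relies on sphericity, and the text does not say what is done if sphericity fails.

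**Working it through.** The documents give no SD, correlation, effect size or power for dyspnea, so there is no planned figure to reproduce. The first step is algebra and needs no assumed SD. The others rest on assumed inputs.

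**Inputs from the documents.** n = 10; two mask levels, two environments, three ratings, so 12 cells per participant and 120 ratings; alpha 0.05. Exercise lasts 10 x (30 + 90) s = 20 minutes, so the 10-minute rating is at mid-session.

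**1. What the main effect estimates.** Average the mask-control difference over environment and call it d1 (before), d2 (10 minutes) and d3 (after). Let d = (d2 + d3)/2 and r = d1/d. Then

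main effect = (d1 + d2 + d3)/3 = d(r + 2)/3.

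| r | Main effect / exercise-phase effect |
|---|---|
| 0 | 2/3 = 0.67 |
| 0.25 | 2.25/3 = 0.75 |
| 0.5 | 2.5/3 = 0.83 |
| 1 | 3/3 = 1.00 |

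The documents do not say whether the mask was on at the pre-exercise rating, so r cannot be narrowed further.

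**2. Whether the test weakens too.** Assume d = 0.8 with exercise SD 1 for the difference, a common correlation rho of 0.3 to 0.7 between readings, and a resting SD of 0.01 to 1. Power is from the noncentral t with 9 df.

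- If r = 0 and resting differences do not vary, effect and SD both shrink by 2/3, so F, p and partial eta squared do not change.
- If resting differences vary as much as exercise ones (r = 0, rho = 0.5), the three-reading effect is 0.8 x 2/3 = 0.533 with SD sqrt((3 + 6 x 0.5)/9) = 0.816. The noncentrality is 0.533/0.816 x sqrt(10) = 2.07 and power is 0.45. For two readings the SD is sqrt((1 + 0.5)/2) = 0.866, the noncentrality is 0.8/0.866 x sqrt(10) = 2.92 and power is 0.74.
- Over all settings, main-effect power is 0.39-0.80 (r = 0), 0.47-0.88 (r = 0.25) and 0.56-0.93 (r = 0.5), against 0.69-0.80 for the two-reading contrast. The three-reading test can therefore be weaker or stronger.

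**3. The planned tests taken together.** Simulation used 40,000 runs in each of 27 settings (r = 0, 0.25, 0.5; rho = 0.3, 0.5, 0.7; resting SD = 0.01, 0.5, 1), with mask x time tested uncorrected on F(2,18).

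| | r = 0 | r = 0.25 | r = 0.5 |
|---|---|---|---|
| Power of mask x time | 0.52-0.91 | 0.31-0.67 | 0.16-0.34 |
| Two-reading contrast significant and mask x time not | 1-35% | 11-52% | 36-65% |

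The second row gives joint probabilities, not probabilities conditional on a significant contrast. It shows how often the trigger for time-specific testing would be absent although the exercise-phase contrast would be significant. In most of those runs the main effect is significant. The contrast is significant with **both** mask and mask x time non-significant in only about 0-9% of runs. At least one of the two planned tests is significant in 0.70-0.94 of runs, although two tests at 5% each carry more than 5% type I error.

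**4. Precision of the missing estimate.** The half-width of the 95% interval for the two-reading contrast is 2.262 x sqrt((1 + rho)/2)/sqrt(10): 0.58 SD at rho = 0.3 and 0.66 SD at rho = 0.7.

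**5. Sphericity.** Four of the seven effects involve time: time, mask x time, environment x time and the three-way term. Each has 2 numerator df. Simulated type I error of the uncorrected mask x time test (60,000 runs):

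- equal exercise SDs, rho 0.3-0.7: 4.9-5.5%; up to 7.3% at rho 0.9;
- exercise SDs 0.7 and 1.3, rho 0.3-0.7: 6.3-7.3%; 7.8-8.3% at rho 0.9;
- Greenhouse-Geisser, all settings: 4.0-5.2%.

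The mask and environment main effects, their interaction and all the 2x2 ANOVAs have 1 df and need no correction.

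**The case against.** The strongest reply is that the plan never calls the three-level mask main effect the effect during exercise. It sets out to compare responses before and during exercise, and the scale is there to record change. A time factor with a resting level fits that purpose, mask x time is the natural test, and it is calculated. All of this stands, and it is why the model should be kept.

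Second, a reader might infer that the mask difference during exercise would go unreported without a significant interaction. The documents do not support that: the post-hoc sentence governs testing and says nothing on whether means or differences at each time are shown. What stands is narrower. No exercise-phase contrast is defined, and no planned test of one exists outside the interaction route. The averaged dyspnea score does not clearly fill the gap, because it is not said to leave out the resting rating.

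Third, a reader might infer that a real mask effect would be missed. The 0-9% figure speaks against that.

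Fourth, silence on sphericity in a short methods text is an omission, not a stated decision to use uncorrected tests. The higher error rates need unequal exercise SDs or a correlation of 0.9. The true departure from sphericity is unknown.

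**Conclusion.** The point holds as a minor limit on estimation. With r below 1, the planned mask main effect understates the exercise-phase effect in mm, to 0.67 of it if the mask has no effect at rest. Unless an interaction is significant, the planned tests give no direct estimate of the quantity in the objective. The ratio is exact algebra, given that the three time levels are the three ratings.

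The loss in detection is small: about 0-9% of runs, under n = 10, an effect of 0.8 SD, correlation 0.3-0.7 and resting SD up to the exercise SD. None of these inputs except n comes from the documents. The sphericity gap is worth about 5% to 8% type I error for time effects, again under assumed SDs and correlations.

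The documents do not support the stronger conclusions that the model is wrong, that the plan misreads its own main effect, or that the dyspnea tests are seriously inflated or underpowered because of this choice.

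**What to change.** - Keep the 2x2x3 model.
- Report the mask-control contrast for the mean of the 10-minute and post-exercise ratings, with a 95% confidence interval, whatever the interaction result. The methods text already describes what happened in the sessions (for example, "one participant chose to ingest water during two of the four HIIIE sessions"), so label the contrast post hoc if results have been seen.
- State that the three-level mask main effect is not to be read as the effect during exercise.
- Apply Greenhouse-Geisser to every effect involving time.
- As clarifications, say which readings form the averaged dyspnea score and whether the mask was on at the pre-exercise and post-exercise ratings.

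The cost is some wording and one extra reported comparison on data already collected. Greenhouse-Geisser lowers mask x time power by about 0.02-0.06 under the assumed inputs, to 0.47-0.89, 0.27-0.63 and 0.14-0.30 for r = 0, 0.25 and 0.5.

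### The Bonferroni follow-up of an interaction names neither its comparisons nor its error term; if it spans all pairs of conditions, it costs power for a mask effect confined to one environment

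*Combined protocol and SAP*

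**What the plan says.** The Objective is "to investigate the effects of surgical mask use during high intensity interval exercise (HIE) on physiological and perceptual responses in hot and temperate environments". The Statistical Analysis section states the main model: "A 2x2 repeated measures ANOVA was performed to investigate statistical differences for all variables across TEMP/CON, TEMP/MASK, HOT/MASK, HOT/CON conditions". Dyspnea is the exception, with a "2x2x3 repeated measures ANOVA being performed for perceived dyspnea data where time was an additional independent variable". Main and interaction effects are both tested at the 0.05 level. The only follow-up rule is that "A Bonferroni post-hoc test was used to determine specific differences with significant interaction effects".

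No list or number of comparisons is given, and no error term. The section names the software but none of its post-hoc settings. No Bonferroni step is described for main effects.

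**The concern.** A Bonferroni adjustment is defined by the number of comparisons it covers, and here that number is open. The model sentence lists all four conditions and nothing later narrows the pairs, so comparing every cell with every other is the natural reading. Most of those pairs do not isolate the mask. Some compare hot with temperate, a condition that the investigators imposed, and some change mask and environment together. Each mask contrast would be charged for all of them.

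With 10 participants, the multiplier can decide whether a mask effect in one environment is declared after the interaction has been found. A reader of the results also cannot tell which multiplier was applied.

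**Working it through.** **Inputs from the document.** There are 10 participants (Participants). Each does all four conditions in a crossover (High Intensity Interval Exercise Trials). Dyspnea has three time points (Perceptual Measurement). Alpha is 0.05 (Statistical Analysis); sidedness is not stated and is taken as two-sided.

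**Assumptions.** The document gives no effect size, SD, correlation or power, so there is no planned figure to reproduce. Effects below are in SDs of the paired mask-minus-control difference. The correlation between the TEMP and HOT paired differences is set at 0 or 0.5. The base case uses separate paired t tests on 9 df.

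**1. Size of the family if it is all pairs.**
- 2x2: C(4,2) = 6. Two pairs are mask v control within an environment, two are hot v temperate, and two are diagonal.
- Dyspnea, mask by environment: 4 cells, 6 pairs.
- Dyspnea, a two-way interaction with time: 6 cells, C(6,2) = 15.
- Dyspnea, three-way: 12 cells, C(12,2) = 66. Of these, 2 environments × 3 times = 6 are matched mask v control pairs, and 4 of the 6 fall during or after exercise.

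**2. Threshold for one contrast.** The per-comparison alpha is 0.05/m, and the smallest significant observed effect is t/√10. Power is from the noncentral t at a true effect of 1.0 SD.

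| m | alpha/m | critical t (9 df) | smallest significant effect (SD) | power |
|---|---|---|---|---|
| 2 | 0.025 | 2.69 | 0.85 | 68% |
| 4 | 0.0125 | 3.11 | 0.98 | 55% |
| 6 | 0.0083 | 3.36 | 1.06 | 47% |
| 66 | 0.00076 | 4.98 | 1.58 | 13.5% |

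**3. The two steps together (simulated).** The mask effect is 1.0 SD in HOT and zero in TEMP. The interaction is tested at 0.05, then the HOT contrast.

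| Correlation | Interaction significant | HOT declared, 6 pairs | HOT declared, Holm over 2 | Lost after a significant interaction, 6 pairs | Lost, Holm over 2 |
|---|---|---|---|---|---|
| 0 | 51% | 35% | 45% | 32% | 12% |
| 0.5 | 80% | 42% | 60% | 47% | 26% |

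The columns agree: 0.51 × 0.68 = 0.35 and 0.80 × 0.53 = 0.42.

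**4. Sensitivity.**
- *Effect size, correlation 0:* at 0.8, 1.0, 1.2 and 1.5 SD, the loss after a significant interaction is 47%, 32%, 19% and 7% with 6 pairs, and 23%, 12%, 6% and 1% with 2. At 1.5 SD, HOT is declared in 0.846 × 0.928 = 79% of trials against 0.846 × 0.987 = 84%, a gap of five points.
- *Effect size, correlation 0.5:* the 6-pair loss is 63% at 0.8 SD and 12% at 1.5 SD.
- *Pooled error term, correlation 0:* at 1.0 SD the loss is 16% with 6 pairs and 6% with 2. In all trials this is 0.515 × 0.842 = 43% against 0.515 × 0.940 = 48%. At 1.5 SD the 6-pair loss is 1%.
- *Mask effect in both environments (HOT 1.0, TEMP 0.5 SD):* the 6-pair loss of the HOT effect is 15% with paired tests and 5% with pooled error.
- *Opposite effects (+0.5 and -0.5 SD):* after a significant interaction, neither mask pair is found in 69% with 6 pairs against 41% with 2.
- *Dyspnea after a three-way interaction, effect only in HOT at the last time:* with 66 pairs it is found in 25% (1.0 SD) and 59% (1.5 SD) using paired tests, or 63% and 96% using pooled error. With the 6 matched mask pairs, the figures are 68% and 94%, or 88% and 99%.

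**5. Error control with the narrower family.** If the interaction is real, at most one of the two mask effects can be zero. With no mask effect anywhere, any false mask finding after a significant interaction occurs in at most 1.7% of trials under Holm over 2. With HOT at 0.8 to 1.5 SD and TEMP null, a false TEMP finding occurs in at most 4.7%.

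**The case against.** The strongest reply is that the document never says all pairs. Neither 6 nor 66 appears in it, and a Bonferroni adjustment over simple effects fits the same sentence. Reading the family from the named software would rest on knowledge of its defaults, which the document does not supply. This stands: all pairs is an inference. It does not remove the point, because the sentence still leaves the family open.

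A reader might also infer that the likely result is a significant interaction with no specific difference. The figures do not support that. At 1.0 SD the 6-pair rule still finds the HOT effect in 68% or 53% of trials with a significant interaction. An interaction without it arises in 16% or 38% of all trials. Part of the missed effect comes from the interaction test itself, which a smaller family leaves unchanged.

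Nor can one say that the mask question goes unanswered. A mask effect of similar size in both environments is a main effect tested at 0.05, and a significant interaction already shows that the mask effect differs by environment. The 66-pair penalty likewise belongs only to a three-way follow-up, not to every dyspnea comparison.

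Finally, the Statistical Analysis section poses its question across all four conditions, so hot v temperate pairs are a legitimate follow-up. That is fair, but they can be described without drawing on the error budget of the mask contrasts.

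**Conclusion.** The point holds in a limited form. The follow-up rule leaves the family and the error term open. On its most natural reading it spends most of its adjustment on pairs that do not bear on the objective. For a 1.0 SD mask effect confined to HOT, with separate paired t tests, the cost is about 10 points of power at correlation 0 (35% v 45%) and 18 at correlation 0.5 (42% v 60%). At correlation 0 it falls to about five points either at 1.5 SD or with pooled error at 1.0 SD. It is largest for dyspnea after a three-way interaction with separate paired tests.

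All of this rests on the all-pairs reading and on effect sizes and correlations that the document does not give. The sentence is still worth changing: naming the mask contrasts is cheap, fits the objective better, and keeps the simulated false mask findings for any one outcome below 5%. It does not address multiplicity across the many outcomes.

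**What to change.** Replace the post-hoc sentence with text along these lines:

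- After a significant mask-by-environment interaction, test mask minus control in TEMP and mask minus control in HOT by paired t tests (9 df), with Holm adjustment over these two.
- For dyspnea, only after a significant interaction that involves mask, test mask minus control at 10 minutes and immediately after exercise in each environment by paired t tests, with Holm over these four. An environment-by-time interaction alone does not open them.
- Report all other pairs as description only.

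The section is written in the past tense, so results may already exist. In that case, present this as a re-analysis with contrasts chosen from the stated objective. Show it beside the post-hoc results already obtained, and state the family and error term that were used for those. Otherwise the narrower family could look like a choice made to gain significance.

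The cost is a few lines of text and a rerun on existing data, with no new participants. The hot-versus-temperate and diagonal pairs lose their post-hoc p-values.
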